#### **4.3.7 Hyperlipidemia**

Prevalence of hyperlipidemia as measured by fasting lipid panel and/or use of lipid-lowering agents at baseline, Days 28, 56 and 180 post-randomization will be compared between groups at each timepoint using a Z-test for binomial proportions (or Barnard's

Exact Unconditional Test as appropriate). For each of the measured components of the fasting lipid panel (e.g. total cholesterol, LDL, HDL, and triglycerides), the proportion of patients in each study arm with measurements outside of normal range (abnormally high for total cholesterol, LDL, and triglycerides; abnormally low for HDL) will also be compared in this manner.

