#### **2.3.3.** Exploratory Objectives are to assess the following:

- 1. Steroid-dose (measured in prednisone-equivalent) on Days 7, 14, 21, 28, 35, 42 and 56.
- 2. Use of topical (skin, GI) agents for acute GVHD therapy.
- 3. Incidence of discontinuation of immune suppression, and immune suppression discontinuation without GVHD or disease progression/recurrence by Days 56, 180, and 365 post-therapy.
- 4. Incidence of EBV-associated lymphoproliferative disorder or EBV reactivation requiring therapy
- 5. Incidence of corticosteroid- and sirolimus-associated complications (collected in all patients):
  - a. Incidence of hyperglycemia (defined as a random glucose >200mg/dL or fasting glucose >126mg/dL) and use of diabetes therapy (use of insulin and/or oral medications to control and/or maintain glucose levels) at baseline, Day 28 and Day 56.
  - b. Change from baseline in functional myopathy score at Day 56 and 6-months post-randomization.
    - i. Hip Flexor and Quadriceps Strength via handheld dynamometer
    - ii. Two Minute Walk Test
    - iii. 5-time Sit-to-Stand
    - iv. Adult Myopathy Assessment Tool (AMAT)
  - c. Incidence of hyperlipidemia as measured by fasting lipid panel at baseline, Days 28, 56 and 180 post-randomization.
  - d. Incidence of post-transplant thrombotic microangiopathy (TMA) by 6 months post-randomization.
- 6. Proportion of patients requiring therapy for CMV-reactivation by day 56 post-randomization.
- 7. Change in patient-reported outcomes from enrollment to Day 56, 6 months and 12 months.
  - a. MD Anderson Symptom Inventory (MDASI)
  - b. FACT-BMT
  - c. MOS Short Form 36 (SF-36)
  - d. PedsQL (Pediatric patients)
- 8. A secondary descriptive analysis will evaluate outcomes for AA3 patients.

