#### 7. Hyperlipidemia

Prevalence of hyperlipidemia as measured by fasting lipid panel and use of lipid-lowering agents at baseline, Days 28, 56 and 180 post-randomization will be compared between groups at each timepoint using a Z-test for binomial proportions (or Barnard's Exact Unconditional test as appropriate).

8. Post-transplant thrombotic microangiopathy

Cumulative incidence of post-transplant thrombotic microangiopathy will be estimated (treating death as a competing risk) and curves will be compared using Gray's test. Estimates and confidence intervals will be provided for 6 months post-randomization.

9. CMV-reactivation

Proportion of patients requiring therapy for CMV-reactivation by Day 56 post-randomization will be compared between treatment groups using a Z-test (or Barnard's Exact unconditional as appropriate).

10. Change in Patient-Reported Outcomes from Enrollment to Day 56, 6 months and 1 year. Participant self-reported measures will be assessed using the MDASI, FACT-BMT, and MOS SF-36 (or PedsQL for Pediatric patients) at enrollment, day 56, 6 months and 1 year. These will be scored according to the recommendations of the developers. Patient reported outcomes at each time point will be summarized using simple descriptive statistics (mean, SD). PRO among survivors at each time point will be compared between treatment arms in an initial analysis using two sample t-statistics. The missing data pattern of the PRO measurements will be examined using graphical techniques and logistic regression models conditional on survival. At each time point, estimates of the difference in PRO between the treatments conditional on survival at that

time point will be obtained using inverse probability of censoring weighting with independent estimating equations to account for missing data.

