### **1.2.2 Accrual Plan and Randomization**

The target sample size of the study is 120 participants with AA1/2 biomarker status. It is expected that 80% of all randomized participants will have AA1/2 status. This requires 150 total participants to be randomized in order to obtain the targeted number of AA1/2 participants.

The estimated accrual period is 2 years.

Participants will be randomized to sirolimus or prednisone treatment in a 1:1 ratio. Randomization is stratified by treatment center using permuted blocks of randomly chosen sizes of 2 or 4.

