The number randomized is determined under the assumption that 80% of randomized participants will have biomarker results indicating standard risk disease (AA1 or 2). Note that 60 analyzable participants per arm (150 randomized) will result in a lower bound of 15% if the success rates in the two populations are equivalent. If sirolimus is 10% worse than the prednisone arm, the lower bound of the confidence interval will exceed 15%. The difference in Day 28 CR/PR rates across the two arms will be reported with its associated 90% confidence interval, however no pre-planned difference or width of confidence interval will be used to indicate failure of either arm or serve as a requirement for consideration of secondary endpoints (i.e. formal non-inferiority will not be declared in this trial). A key secondary endpoint is the proportion of participants in CR/PR with a steroid dose of  $\leq 0.25$  mg/kg by Day 28. Of the 95 placebo participants, 22.1% (95% CI 13.8% - 30.5%) achieved a CR/PR by Day 28 and were receiving  $\leq 0.25$  mg/kg. This estimate may not be reliable, however, as the taper for BMT CTN 0802 suggested a minimum of 0.25 mg/kg on Day 28; as such, this may be an underestimate of the true rate. Using the upper end of the confidence interval, sixty participants per arm would provide 80.6% power (two-sided 5% type 1 error rate) to test for a difference of 25% between the two groups (30% Prednisone vs. 55% Sirolimus).

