## **2.9 General Analysis Guidelines**

Continuous variables will be described using the mean, standard deviation, median, and range. Categorical variables will be described using frequencies and proportions. All statistical tests will be two-sided at a 0.05 significance level unless otherwise specified.

Any changes to the planned analyses and addition of any ad-hoc analyses will be documented in the final analysis report with justification given for the changes. If it is a change to analysis of an existing endpoint, the change should be clearly stated in the exhibit. If a new endpoint or analysis is performed, it should be included as a supplemental exhibit.

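### The Day 28, 56 and 180 hyperlipidemia comparisons are valid but do not use baseline lipid status, which gives up precision if baseline abnormality is present and persists; the wording also shifts between incidence and prevalence

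*SAP*

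**What the plan says.** Protocol 2.3.3 item 5c gives the objective as "Incidence of hyperlipidemia as measured by fasting lipid panel at baseline, Days 28, 56 and 180 post-randomization", and SAP 1.1.3 repeats it. The analysis sections use a different term. Protocol 5.2.6 item 7 analyses "Prevalence of hyperlipidemia as measured by fasting lipid panel and use of lipid-lowering agents"; SAP 4.3.7 analyses "Prevalence of hyperlipidemia as measured by fasting lipid panel and/or use of lipid-lowering agents". Besides the change from incidence to prevalence, *and* in the Protocol has become *and/or* in the SAP for lipid-lowering drugs.

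In the Protocol this measure "will be compared between groups at each timepoint using a Z-test for binomial proportions", with Barnard's test as the alternative, and the SAP specifies the same. SAP 2.9 sets the level: "All statistical tests will be two-sided at a 0.05 significance level unless otherwise specified".

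Baseline information exists. Protocol 3.3.5 says that lipid values and lipid-lowering drugs are collected. SAP Exhibit 1501-19 opens with a table of status at randomization by arm, overall and per lipid component, with p-values. The Day 28, 56 and 180 tables that follow are separate cross-sections.

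**The concern.** Two things need attention.

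First, the term in the objective and the term in the analysis differ, so a reader cannot be sure whether the result is meant as new cases or as status at a visit.

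Second, a participant who enters with an abnormal panel, or already on a lipid-lowering drug, is likely to be counted as a case at later visits in either arm. Such participants add variation to the between-arm difference that baseline status could explain. The SAP uses baseline information for comparable endpoints: topical therapy (4.3.2) is compared among participants using none at entry, and myopathy (4.3.6) is analysed as change from baseline.

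At stake is the precision of a comparison on a recognised sirolimus toxicity. Protocol 2.5.3 lists hyperlipidemia among the common ones, above 20%.

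**Working it through.** **Inputs from the documents.** 60 analysed per arm (SAP 2.1), 1:1 allocation (SAP 1.2.2), two-sided 5% (SAP 2.9). Protocol 2.5.3 reports that 42% to 52% of patients in the sirolimus arms of Phase III studies needed drug treatment for new-onset hypercholesterolemia.

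**Assumptions not in the documents.** Baseline prevalence b = 20%, 40% or 60%. New onset among those clear at baseline: qS = 47% on sirolimus (the midpoint of 42% to 52%, which is a treatment rate and only a stand-in for an abnormal panel) and qP = 25% on prednisone. Persistence r of baseline abnormality: 100% first, then varied.

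**The plan's own power figure.** None is given for lipids. The only one is 80.6% for the key secondary endpoint (30% vs 55%, 60 per arm). With power = Φ[(d − 1.96·SE0)/SE1], where SE0 is pooled and SE1 unpooled:

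- SE0 = √(2 × 0.425 × 0.575 / 60) = 0.0903
- SE1 = √((0.30 × 0.70 + 0.55 × 0.45) / 60) = 0.0873
- Power = Φ[(0.25 − 0.1769) / 0.0873] = Φ(0.837) = 79.9%

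This is close to 80.6%; the unpooled version gives 81.7%. The same formula is used below.

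**Visit prevalence.** With equal persistence in both arms, prevalence = b·r + (1 − b)·q, so the between-arm difference is (1 − b)(qS − qP). With r = 100% and b = 40%:

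- Sirolimus: 0.40 + 0.60 × 0.47 = 68.2%
- Prednisone: 0.40 + 0.60 × 0.25 = 55.0%
- Difference: 13.2 points

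**Where the precision goes (b = 40%, r = 100%).** A baseline-stratified risk difference targets the same 13.2 points, 0.60 × 22 + 0.40 × 0. What changes is the standard error:

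- Unadjusted: √((0.682 × 0.318 + 0.55 × 0.45) / 60) = 0.0880; 0.132 / 0.0880 = 1.50
- Stratified: 0.60 × √((0.47 × 0.53 + 0.25 × 0.75) / 36) = 0.0661; 0.132 / 0.0661 = 2.00

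**Power at full persistence.** The simulated columns use 40,000 trials per scenario; the stratified test is Cochran-Mantel-Haenszel (CMH).

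| b | Prevalence, sirolimus / prednisone | Difference (points) | Planned test, formula | Planned test, simulated | Stratified, simulated | New onset only, formula (n per arm) |
|---|---|---|---|---|---|---|
| 20% | 57.6% / 40.0% | 17.6 | 48.7% | 50.4% | 61.8% | 61.5% (48) |
| 40% | 68.2% / 55.0% | 13.2 | 31.6% | 32.2% | 49.6% | 49.4% (36) |
| 60% | 78.8% / 70.0% | 8.8 | 19.5% | 20.3% | 35.0% | 35.1% (24) |

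At b = 0 the planned and new-onset analyses coincide (71.4%).

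**Varying persistence (simulated; b = 20% / 40% / 60%).**

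| Still abnormal, sirolimus vs prednisone | Planned | Stratified | New onset only |
|---|---|---|---|
| 90% vs 90% | 50.8 / 31.7 / 17.9% | 58.2 / 41.2 / 24.2% | 62.2 / 50.0 / 36.0% |
| 85% vs 85% | 50.7 / 31.6 / 17.3% | 56.4 / 38.5 / 21.1% | 62.2 / 50.1 / 35.8% |
| 95% vs 75% | 67.7 / 66.1 / 68.1% | 73.7 / 77.0 / 80.8% | 61.8 / 50.3 / 35.8% |
| 90% vs 60% | 75.9 / 80.8 / 86.1% | 79.0 / 85.7 / 91.4% | 62.2 / 50.0 / 36.1% |

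The stratified test had more power than the planned one in every effect scenario. With no treatment effect (20% new onset in both arms, equal persistence), the type I error was 4.9% to 5.7% for the planned test and 4.8% to 5.0% for the stratified test.

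**Timing of the baseline panel.** Protocol 4.4 allows it up to 96 hours after enrollment, which is the same step as randomization. Protocol 2.5.1 requires the first dose within 24 hours of randomization. A panel drawn at the 96-hour limit therefore follows the first dose by at least 96 − 24 = 72 hours.

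**The case against.** The strongest case on the other side is that the plan does what it means to do. An incidence listed at baseline as well as later cannot mean new onset; it reads as status at each visit. Protocol 3.3.5 supports this by defining the comparison as the proportion outside the normal range for each lipid component, and SAP 4.3.5 uses incidence in the same loose way for hyperglycemia. That stands. A reader might infer that new onset is the stated objective and has no analysis; the documents do not support that, and the defect there is one of terminology.

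A reader might also infer that baseline status is ignored. It is not: Exhibit 1501-19 tabulates and tests it by arm, so an imbalance would be visible. It is only left out of the later comparisons. Nor does chance imbalance make the planned test biased; randomization covers it, and the type I error is close to nominal.

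A third tempting reading is that counting only new cases would be the more powerful test. That holds if treatment acts only in participants clear at baseline. If it also affects whether abnormal participants stay abnormal, the order reverses: at 95% vs 75% and b = 20%, the planned test has 67.7% power and new onset alone 61.8%.

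Finally, adjusting on a panel drawn after dosing would condition on a post-randomization value and could harm a comparison that is now valid. This stands, and the fix has to deal with it.

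**Conclusion.** The point holds as a minor one. The incidence/prevalence and *and*/*and/or* wording should be reconciled. The post-baseline comparisons leave out a covariate that is already collected, which loses precision when baseline abnormality is present and tends to persist.

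How much is lost cannot be read from the documents. Under the assumptions above with full persistence, the simulated gain from stratifying is about 11 points of power at 20% baseline prevalence (50.4% to 61.8%) and 17 points at 40% (32.2% to 49.6%). At 85% persistence in both arms it is about 6 and 7 points. With no baseline abnormality there is nothing to gain.

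It would go too far to say that the plan demonstrably loses power or dilutes a known effect. The endpoint is exploratory, has no power statement or decision rule, and the planned test is valid.

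**What to change.** Make the same change in SAP 4.3.7, Protocol 5.2.6 item 7 and Exhibit 1501-19:

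- Keep the all-participant prevalence table at every visit.
- Make the between-arm comparison at Days 28, 56 and 180 a Mantel-Haenszel risk difference with a CMH test, stratified by baseline status, overall and for each lipid component.
- Define baseline status from panels drawn before the first dose, and add a sensitivity analysis that also admits later panels.
- Report new onset among participants normal and untreated at baseline as supportive description, not as a more powerful test.
- Use one term, incidence or prevalence, in objective and analysis, and choose between *and* and *and/or* for lipid-lowering drugs.

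The cost is wording in both documents, revised table shells and slightly more analysis; no new data are needed. Replacing the planned test rather than adding to it leaves the number of between-arm tests at these visits unchanged in the main analysis. The main drawback is that some participants may lack a pre-dose panel, so the SAP should say in advance how they are handled.

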# Hyperlipidemia

Incidence of hyperlipidemia as measured by fasting lipid panel at baseline, Days 28, 56 and 180 post-randomization. The proportion of patients in each study arm with elevation outside of normal range for each of the measured components of the fasting lipid panel (e.g. total cholesterol, LDL, HDL, and triglycerides) will be compared. Lipid parameters and use of lipid-lowering medications will be collected.

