### **4.3 Analysis of the Exploratory Endpoints**

Since this is a phase II trial with many secondary and exploratory endpoints, no explicit control for multiplicity will be incorporated; rather a significance level of 5% will be used for all comparisons on these outcomes.

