**Exhibit 1501-19: Hyperlipidemia**

Hyperlipidemia Status at Randomization by Treatment Group				
Condition		Sirolimus (N=) N (%)	Prednisone (N=) N (%)	P-value*
Hyperlipidemia	Yes	XX (XX.X%)	XX (XX.X%)	X.XXX
	No	XX (XX.X%)	XX (XX.X%)	
	Not Evaluable	XX	XX	
High Total Cholesterol	Yes	XX (XX.X%)	XX (XX.X%)	X.XXX
	No	XX (XX.X%)	XX (XX.X%)	
	Not Evaluable	XX	XX	
High LDL	Yes	XX (XX.X%)	XX (XX.X%)	X.XXX
	No	XX (XX.X%)	XX (XX.X%)	
	Not Evaluable	XX	XX	
Low HDL	Yes	XX (XX.X%)	XX (XX.X%)	X.XXX
	No	XX (XX.X%)	XX (XX.X%)	
	Not Evaluable	XX	XX	
High Triglycerides	Yes	XX (XX.X%)	XX (XX.X%)	X.XXX
	No	XX (XX.X%)	XX (XX.X%)	
	Not Evaluable	XX	XX	

Hyperlipidemia Status at Day 28 by Treatment Group				
Condition		Sirolimus (N=) N (%)	Prednisone (N=) N (%)	P-value*
Hyperlipidemia	Yes	XX (XX.X%)	XX (XX.X%)	X.XXX
	No	XX (XX.X%)	XX (XX.X%)	
	Not Evaluable	XX	XX	
High Total Cholesterol	Yes	XX (XX.X%)	XX (XX.X%)	X.XXX
	No	XX (XX.X%)	XX (XX.X%)	
	Not Evaluable	XX	XX	
High LDL	Yes	XX (XX.X%)	XX (XX.X%)	X.XXX
	No	XX (XX.X%)	XX (XX.X%)	
	Not Evaluable	XX	XX	
Low HDL	Yes	XX (XX.X%)	XX (XX.X%)	X.XXX
	No	XX (XX.X%)	XX (XX.X%)	

	Not Evaluable	XX	XX	
High Triglycerides	Yes	XX (XX.X%)	XX (XX.X%)	X.XXX
	No	XX (XX.X%)	XX (XX.X%)	
	Not Evaluable	XX	XX	

Hyperlipidemia Status at Day 56 by Treatment Group				
Condition		Sirolimus (N=) N (%)	Prednisone (N=) N (%)	P-value*
Hyperlipidemia	Yes	XX (XX.X%)	XX (XX.X%)	X.XXX
	No	XX (XX.X%)	XX (XX.X%)	
	Not Evaluable	XX	XX	
High Total Cholesterol	Yes	XX (XX.X%)	XX (XX.X%)	X.XXX
	No	XX (XX.X%)	XX (XX.X%)	
	Not Evaluable	XX	XX	
High LDL	Yes	XX (XX.X%)	XX (XX.X%)	X.XXX
	No	XX (XX.X%)	XX (XX.X%)	
	Not Evaluable	XX	XX	
Low HDL	Yes	XX (XX.X%)	XX (XX.X%)	X.XXX
	No	XX (XX.X%)	XX (XX.X%)	
	Not Evaluable	XX	XX	
High Triglycerides	Yes	XX (XX.X%)	XX (XX.X%)	X.XXX
	No	XX (XX.X%)	XX (XX.X%)	
	Not Evaluable	XX	XX	

Hyperlipidemia Status at Day 180 by Treatment Group				
Condition		Sirolimus (N=) N (%)	Prednisone (N=) N (%)	P-value*
Hyperlipidemia	Yes	XX (XX.X%)	XX (XX.X%)	X.XXX
	No	XX (XX.X%)	XX (XX.X%)	
	Not Evaluable	XX	XX	
High Total Cholesterol	Yes	XX (XX.X%)	XX (XX.X%)	X.XXX
	No	XX (XX.X%)	XX (XX.X%)	
	Not Evaluable	XX	XX	
High LDL	Yes	XX (XX.X%)	XX (XX.X%)	X.XXX

	No	XX (XX.X%)	XX (XX.X%)	
	Not Evaluable	XX	XX	
Low HDL	Yes	XX (XX.X%)	XX (XX.X%)	X.XXX
	No	XX (XX.X%)	XX (XX.X%)	
	Not Evaluable	XX	XX	
High Triglycerides	Yes	XX (XX.X%)	XX (XX.X%)	X.XXX
	No	XX (XX.X%)	XX (XX.X%)	

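### The four fasting lipids are measured as values but compared between arms only as inside or outside the normal range; a comparison of the values should be added.

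*SAP*

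**What the plan says.** SAP 4.3.7 plans two kinds of comparison at baseline and Days 28, 56 and 180. One is an overall yes/no hyperlipidemia status, which counts an abnormal panel and/or lipid-lowering drug use. The other takes each of the four lipids and compares "the proportion of patients in each study arm with measurements outside of normal range", meaning high for total cholesterol, LDL and triglycerides and low for HDL. Both use a Z test, or Barnard's test where appropriate.

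Exhibit 1501-19 follows this. A row such as "High Total Cholesterol" is split into Yes, No and Not Evaluable, with counts, percentages and a p-value. There is no mean, median, range or change from baseline.

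Protocol 3.3.5 (Hyperlipidemia) asks for the same out-of-range comparison and then states: "Lipid parameters and use of lipid-lowering medications will be collected". The measured values will therefore be in the database.

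The preceding section, SAP 4.3.6, treats another exploratory complication differently. Functional myopathy scores get medians, ranges and Wilcoxon tests of change from baseline.

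On error rates, SAP 4.3 sets no multiplicity control: "rather a significance level of 5% will be used for all comparisons on these outcomes". SAP 2.9 adds: "All statistical tests will be two-sided at a 0.05 significance level unless otherwise specified".

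**The concern.** Hyperlipidemia is listed in the sirolimus toxicity table (Protocol 2.5.3) among events seen in more than 20% of patients, and Protocol 1.1 names it as a corticosteroid toxicity too. Many patients in both arms may therefore be out of range. In that setting a yes/no cut is a blunt measure: a patient just above the limit and one far above it count the same, while a small move across the limit counts in full.

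With 60 or fewer patients per arm, the trial could miss a lipid difference that its own data contain. It would also report that difference only as a change in percentages, not as the size of the lipid change. Neither document explains why lipids are cut when myopathy scores are not.

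**Working it through.** **Inputs from the documents.** SAP 1.2.2: "The target sample size of the study is 120 participants with AA1/2 biomarker status" and "Participants will be randomized to sirolimus or prednisone treatment in a 1:1 ratio", hence 60 per arm. Tests are two-sided at 5% (SAP 2.9 and 4.3). The planned test is the Z test of proportions (SAP 4.3.7).

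**Not in the documents, so assumed.** The lipid shift between arms, its SD, the share of prednisone patients out of range, and attrition at the lipid visits. Values are taken as normal (after a log transform if needed) with equal SD.

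**Check on the plan's own figure.** The only power figure given is 80.6% for 30% against 55% with 60 per arm (SAP 2.1), for the key secondary endpoint. Summing the two binomial distributions over all outcomes where the pooled Z statistic exceeds 1.96 gives 80.6%; the closed-form pooled approximation gives 79.9%. The stated figure is reproduced, and the same enumeration is used below.

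**Formulas.** With out-of-range rates p0 (prednisone) and p1 (sirolimus):

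- Shift in SD units: d = Φ⁻¹(p1) − Φ⁻¹(p0).
- t test: noncentral t with 118 degrees of freedom and noncentrality d × √(60/2).
- Z test: sum of P(x)P(y) over outcomes with |x − y|/60 ÷ √(2q(1 − q)/60) > 1.96, where q = (x + y)/120.

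Example, 20% against 40%: d = −0.253 + 0.842 = 0.59 and noncentrality = 0.588 × 5.477 = 3.22. The t test has 89.2% power and the Z test 68.4%, so the loss is 89.2 − 68.4 = 20.8 points.

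| p0 vs p1 | d | Z test | t test | Loss vs t | Rank-sum (simulated) | Loss vs rank-sum |
|---|---|---|---|---|---|---|
| 10% vs 25% | 0.61 | 58.5% | 91.0% | 32.5 | 89.5% | 31.0 |
| 20% vs 40% | 0.59 | 68.4% | 89.2% | 20.8 | 88.2% | 19.8 |
| 30% vs 50% | 0.52 | 61.8% | 81.3% | 19.5 | 78.8% | 17.0 |
| 40% vs 60% | 0.51 | 61.2% | 78.6% | 17.4 | 77.3% | 16.1 |
| 60% vs 80% | 0.59 | 68.4% | 89.2% | 20.8 | 86.7% | 18.3 |

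These five scenarios give 17 to 33 points against the t test and 16 to 31 against the rank-sum test. Filling in the whole region (0.5 to 0.6 SD, p0 10 to 60%) widens the t-test range slightly, to 15 to 36. With 45 per arm, an assumed attrition, the five scenarios give 20 to 32 points.

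**Other shifts, 60 per arm, p0 from 20 to 80%, loss against the t test.**

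- 0.2 SD: 4 to 8 points
- 0.3 SD: 10 to 19 points (t-test power only 37%)
- 0.8 SD: 5 to 26 points
- 1.0 SD: 1 to 13 points

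Over a wide grid (0.2 to 1.0 SD, p0 5 to 90%) the loss runs from about 1 to 57 points. It is never a gain.

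**Lipid-lowering drugs.** Protocol 2.5.3 reports that 42 to 52% of patients in the sirolimus arms of Phase III studies needed treatment for new hypercholesterolemia. An illustrative simulation assumes a 0.5 SD shift, p0 of 20 to 50%, 50 to 80% of out-of-range patients treated, and a 1 SD fall on treatment.

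- t test on values as measured: 66 to 72%, down from 77%.
- Component Z test on the same values: 29 to 48%, so the gap is about 18 to 41 points.
- A status that also counts drug use, like the plan's overall comparison: 53 to 58%, so the gap is about 8 to 19 points.

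Under similar assumptions a rank-sum test on values as measured keeps about 13 to 36 points over the component Z test. Ranking all treated patients at the top is less safe: with 60% of prednisone patients out of range it has about 48 to 51% power against 50 to 51% for the Z test, which is no gain.

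**The case against.** The strongest counter-argument is that the SAP does what the protocol asks. The objective is the incidence of hyperlipidemia, a yes/no state, and Protocol 3.3.5 itself says the out-of-range proportions will be compared for each component. A reader might infer that those four tests should be replaced. The documents do not support that: replacement would drop a protocol-specified comparison and need a protocol change or a documented departure. This stands in full, and it limits the remedy to an addition.

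Second, SAP 2.9 says continuous variables will be described by mean, SD, median and range, and SAP 5 calls the shells illustrative. It would therefore be too strong to say that the values can never appear. What stands is narrower: neither SAP 4.3.7 nor its exhibit applies that general line to lipids, and no comparison of values is specified.

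Third, one might fault the cut because normal limits vary by age and site. That is weak. An age-specific limit is itself a form of age adjustment, which pooled raw values lose, and stratifying randomization by center should roughly balance site differences.

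Fourth, steroids also raise lipids, so the shift between arms may be small, and treatment lowers the measured values. Both are fair. The first moves the case towards the 0.3 SD line, where both tests have little power. The second means a value comparison needs a stated rule for drug use; the planned component comparisons have no such rule either.

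Finally, the endpoint is exploratory (Protocol 5.2.6). No primary or key secondary conclusion depends on it.

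**Conclusion.** The concern holds as a minor point. The component lipids are compared only on a dichotomised scale although the values are collected and the plan already uses Wilcoxon tests for comparable data. For an assumed shift of 0.5 to 0.6 SD with 10 to 60% of prednisone patients out of range and 60 per arm, the cost is about 17 to 33 points of power against a t test and 16 to 31 against a rank-sum test.

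A reader might take such a range as a property of this plan. It is not: neither document gives a lipid effect, SD or out-of-range rate, and the loss depends on all three. Nor does the plan fall short of a promise, since no power is stated for lipids. The direction is firm for untreated normal values; the size is conditional. Lipid-lowering treatment reduces the power of a value comparison, and its advantage over a status that counts drug use, but under the assumptions tried it does not remove the gain when values are analysed as measured.

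**What to change.** Keep the four out-of-range comparisons and the overall hyperlipidemia comparison as they are. Then:

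1. Add to SAP 4.3.7 a between-arm Wilcoxon rank-sum comparison of each measured lipid at Days 28, 56 and 180. Change from baseline, as in SAP 4.3.6, is an alternative. Protocol 4.4 allows the baseline panel up to 96 hours after enrollment while treatment starts within 24 hours, so some baselines may follow the first doses. Comparing the values themselves avoids that.
2. Add median and range by arm and visit to Exhibit 1501-19.
3. Report lipid-lowering drug use by arm beside these rows, and state in advance how values on treatment are analysed: for example, as measured, with a sensitivity analysis. Top-ranking treated patients should not be the only analysis.

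The cost is SAP text and table rows. No new data, visits or patients are needed, and because nothing in the protocol is removed, the protocol comparison is unaffected. The price is twelve further exploratory p-values (4 lipids × 3 visits) without multiplicity control, to be read as such, and the need to settle the drug-use rule before the data are seen.
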